## 4.0 Test Schedule

### 4.1 Study Calendar

| Tests and procedures                       | Pre-registration | Screening
≤14 days
prior to
registration | Cycle 1
Day 1 | Cycle 2
Day 1
(±5days) | Cycle 3
Day 1
(±5days) | Cycle 4
Day 1 and
subsequent
cycles
(±5days) | End of
Treatment  |
|--|------------------|---|------------------|------------------------------|------------------------------|--|----------------------------------|
| Window                                     |                  |   |                  |                              |                              |  |                                  |
| History and exam,
Weight, PS            |                  | X   | X                | X                            | X                            | X  | X                                |
| Height                                     |                  | X   |                  |                              |                              |  |                                  |
| Hematology: CBC
with differential       |                  | X   | X    | X                            | X                            | X  | X                                |
| Serum chemistry                |                  | X   | X    | X                            | X                            | X  | X                                |
| Urinalysis                                 |                  | X   | X    | X                            | X                            |  |                                  |
| Serum pregnancy
test (if applicable)    |                  | X                                     |                  |                              |                              |  |                                  |
| Coagulation panel              |                  | X   | X                |                              |                              |  |                                  |
| 12-lead EKG                    |                  | X   |                  |                              |                              |  |                                  |
| Echocardiogram                             |                  | X   |                  |                              |                              |  |                                  |
| Ophthalmologic
examination  |                  | X   |                  | X                            | X                            | X  | X                                |

 End of treatment visit should be at least 21 days from last dose of study drug.

 Need not be repeated if performed within 14 days of Cycle 1 Day 1

 Albumin, alkaline phosphatase, total bilirubin, bicarbonate, BUN, calcium, chloride, creatinine, glucose, LDH, phosphorus, potassium, total protein, SGOT [AST], SGPT [ALT], sodium, magnesium. TSH (at baseline only)

 Pregnancy test must be performed ≤7 days prior to registration

 Coagulation panel: INR or PT and PTT or aPTT.

 Baseline and as clinically indicated

 A detailed ophthalmologic examination (visual acuity, IOP, Schirmer test and slit lamp) will be done for all patients during screening ≤ 28 days before the start of study treatment, as indicated during the study. During treatment, ophthalmologic examination (visual acuity and slit lamp only) can be performed ≤7 days before planned anetumab ravtansine infusion and at the safety follow-up exam. The IOP measurement is to be repeated during anetumab ravtansine therapy if the patient receives steroid eye drops for ≥10 days as treatment for corneal epitheliopathy. This measurement is performed at 2 weeks and 6 weeks after the initiation of steroid treatment. If IOP increases by <7 mmHg, the frequency of IOP

| Tests and procedures  | Pre-registration | Screening ≤14 days prior to registration | Cycle 1 Day 1  | Cycle 2 Day 1 | Cycle 3 Day 1 | Cycle 4 Day 1 and subsequent cycles | End of Treatment  |
|---|------------------|--|----------------|---------------|---------------|-------------------------------------|-------------------------------|
| Window  |                  |  |                | (±5days)      | (±5days)      | (±5days)                            |                               |
| Adverse event evaluation  |                  | X  | X  | X             | X             | X                                   | X                             |
| Tumor measurements    |                  | X  |                |               | X             |                                     | X                             |
| Mandatory tissue (archival or fresh biopsy) for MSLN determination  | X                |  |                |               |               |                                     |                               |
| Mandatory Blood for Biomarker study                                |                  | X  |                |               | X             |                                     | X                |
| Anetumab Raptansine administration followed by Atezolizumab Administration      |                  |  | X              | X             | X             | X                                   |                               |

evaluation can be reduced to every 4 months. If IOP increases by  $\geq 7$  mmHg, a medical management plan with follow-up IOP evaluations will be initiated after consultation with an ophthalmologist and investigator. The Schirmer test is performed at C3D1 and C5D1. All these tests may be repeated during treatment at the investigator's discretion.

 Contrast-enhanced CT/MRI is acceptable as a baseline scan if done within 28 days before C1D1. Visit window of  $\leq 7$  days is allowed. Tumor measurements are repeated every odd cycle starting with Cycle 3. Documentation (radiologic) must be provided for patients removed from study for progressive disease.

 Mandatory biopsy will be collected before treatment if archival tissue ( $\leq 12$  months of registration) not available. See Section 17.

 Mandatory blood will be collected before treatment, every odd cycle starting with cycle C3D1 (in conjunction with imaging, for efficacy) and EOT. See section 14.

 Optional blood sample collection at Disease Progression. See section 14 for further details.

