**Schema**

**Study Participants: Limited to Mayo Clinic**

**Phase I only: Prior to discussing protocol entry with the patient, call the MCCC Registration Office at [REDACTED] for dose level and to ensure that a place on the protocol is open to the patient.**

Anetumab ravtansine, 3+3 dose-escalation from 4.5-6.5 mg/kg IV every 3 weeks-cycle  
 Atezolizumab, 1200 mg IV every 3 weeks-cycle

\*unless otherwise specified

 Cycle length = 21 days

If a patient is deemed ineligible or a cancel, please refer to Section 13.0 for follow-up information.

|  |  |
|--|--|
| 
Generic name: Atezolizumab
         Brand name(s): Tecentriq®
         Mayo Abbreviation: ATEZOLIZUMAB
         Availability: Commercial supply
 | 
Generic name: Anetumab ravtansine
         Brand name(s):
         Mayo Abbreviation: ANETUMAB
         RAVTANSINE
         Availability: Supplied by sponsor Bayer
 |
|--|--|

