**Study Design**

This is a non-randomized dose escalation Phase I study designed to determine the maximum tolerated dose (MTD) and dose-limiting toxicities of anetumab ravtansine (which will be dose-escalated) in combination with atezolizumab (administered at the standard fixed dose) in the treatment of advanced, treatment-refractory mesothelin expressing NSCLCs. This phase of the study uses a standard cohort 3+3 dose-escalation design. The patients will be treated with standard dose atezolizumab along with starting dose level 1 of anetumab ravtansine. Subsequent patient cohort(s) will be enrolled depending on the safety and tolerability of the initial cohort. If <33% patients treated at Dose Level 1 experience dose-limiting toxicity (DLT) by the end of first treatment cycle (21 days), then next cohort of 3 patients will be enrolled and treated at Dose Level 2. The MTD is defined as the maximum dose level at which  $\leq 1/6$  patients have DLTs. If DLT meets the stopping boundaries set by the above dose escalation algorithm at dose level 1 (for example, more than 1 out of 3 patients or more than 1 out of 6 patients), the next cohort of three patients will be entered at a dose level of -1. Further dose re-escalation will depend on the toxicity profile observed at dose level -1, and re-evaluation of the regimen by the study team may be done. A subsequent phase II study will be implemented once the recommended Phase 2 dose (RP2D) is ascertained. Anetumab ravtansine will be given IV once every 3 weeks and is subject to dose-escalation and atezolizumab is administered as a one-hour infusion every 3 weeks.

| Number of Patients | Cohort Level | Anetumab ravtansine (mg/kg) Q3W | Atezolizumab (mg) Q3W |
|--------------------|--------------|---------------------------------|-----------------------|
| 3-6                | -1           | 4.5                             | 1200 mg               |
| 3-6                | 1*           | 5.5                             | 1200 mg               |
| 3-6                | 2            | 6.5                             | 1200 mg               |

\*Starting dose  
 3+3 design; 3-6 pts/dose level. Total 6-12 patients in phase I.  
 Dose level I is starting dose level

|   |   |
|---|---|

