### 7.2 Determination of Maximum Tolerated Dose (MTD)

In Phase I, dose escalation of anetumab ravtansine in combination with Atezolizumab will be performed according to the standard 3+3 design of dose cohorts. Dose escalation decisions will be based on the incidence of Treatment Emergent Adverse Events (TEAEs) observed after Cycle 1 (C1) that fulfills the criteria for a DLT. If a clinically significant TEAE related to anetumab ravtansine is observed more frequently after C1, then this event may be declared a DLT at the investigators' discretion in consultation with the sponsor. If a clinically significant TEAE related to atezolizumab is observed more frequently, or with greater severity than what has been reported in the prescribing information or in the literature, this event also may be declared a DLT at the discretion of investigators in consultation with the sponsor.

At least 3 subjects in each cohort need to provide sufficient safety data after the first treatment cycle (21 days) before a decision can be made whether it is safe to proceed to the next dose level of anetumab ravtansine. To be evaluable for a dose escalation decision, subjects must complete one treatment cycle in their assigned dose cohort; receive one complete infusion of each treatment (anetumab ravtansine and atezolizumab). If a DLT occurs in 2 out of 3 subjects at a given dose level (or in 2 of 4 subjects, if the 4th subject has been enrolled), or in 2 out of up to 6 subjects in the Phase II portion at a given dose level, then dose escalation will stop and the current dose will be declared the non-tolerable dose.

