#### 13.6 Inevaluable patients

If a patient fails to complete the first cycle (21 days) of treatment for reasons other than toxicity, the patient will be regarded as inevaluable and will be replaced during the phase I portion of the trial.

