### 16.2 Phase I Study Design

The primary endpoint of the phase I portion of this trial is to estimate the MTD of anetumab ravtansine combined with atezolizumab. A standard 3+3 phase I design will be utilized. Three patients will be treated at each dose level and observed for a minimum of three weeks (i.e. one full cycle) before new patients are treated. Doses will not be escalated in any individual patient.

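### In phase I the ±5-day window on Cycle 2 Day 1 lets both drugs be given again on day 17, inside the 21-day DLT observation period

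*Combined protocol and SAP*

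**What the plan says.** The calendar in section 4.1 carries the column heading "Cycle 2 Day 1 (±5days". The row "Anetumab Raptansine administration followed by Atezolizumab Administration" is marked under that column and has no dosing window of its own. Footnote 7 says that the on-treatment eye examination "can be performed ≤7 days before planned anetumab ravtansine infusion". The calendar serves both phases.

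The first-cycle observation is given as 21 days in several places:

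- Schema, footnote 1: "Cycle length = 21 days".
- Synopsis, Study Design: DLTs are judged "by the end of first treatment cycle (21 days").
- Section 7.2: "At least 3 subjects in each cohort need to provide sufficient safety data after the first treatment cycle (21 days").
- Section 13.6: a patient who "fails to complete the first cycle (21 days) of treatment" for reasons other than toxicity is replaced.
- Section 16.2: each group of three is "observed for a minimum of three weeks (i.e. one full cycle) before new patients are treated".
- Sections 16.24 and 16.29a also use 21 days, counted from the start of treatment or drug administration.

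Sections 7.6 and 16.621 define the DLT period only as Cycle 1 or the first cycle, without a number of days.

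**The concern.** The ±5 days apply to a column that contains an infusion, so they move the dose as well as the visit. The early edge of the window falls before the 21-day observation has ended. Sections 4, 7, 8 and 16 contain no rule that keeps the two apart.

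The phase I primary endpoint, the MTD, rests on DLT counts in 3 to 6 patients per level. Under 16.26 and 16.27 the step from one to two DLTs in six means that the MTD has been exceeded. A single event that arose after two doses can therefore move the recommended dose down a level, for example from 6.5 to 5.5 mg/kg. Section 1.22 warns, from single-agent data, that starting below 6.5 mg/kg could reduce the potential for benefit.

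There is also a direct safety issue. A patient can receive a second dose of an untested combination before the observation of the first is complete.

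**Working it through.** **Dates, with Cycle 1 Day 1 as day 1**

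- Nominal Cycle 2 Day 1: 1 + 21 = day 22. Earliest: 22 − 5 = day 17.
- Time on the first dose alone: 16 days. Days 17 to 21, which are 5 of the 21 observation days, follow a second dose.
- Earliest Cycle 2 slit-lamp examination: 17 − 7 = day 10, against 22 − 7 = day 15 with on-time dosing.
- Cycle 2 Day 1 is the only scheduled adverse-event and laboratory visit between Cycle 1 Day 1 and Cycle 3 Day 1. If it falls on day 17, the next is day 43 − 5 = 38 by the nominal calendar, or 17 + 21 − 5 = day 33 if windows run from the previous infusion. The text does not say which applies.

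**Does any other rule block a day-17 dose?** The every-3-weeks schedule is the nominal interval that the window modifies. The 21-day rule in 16.2 governs when new patients may be treated, and 16.24 governs how long each patient is watched. Section 7.2 requires one completed cycle and one full infusion of each drug; 16.29a requires drug administration and 21 days. A patient redosed on day 17 and followed through day 21 meets the 21-day requirement. None of these rules says that the 21 days must be free of a second dose.

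**Exposure (illustration)**

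Input: ADC terminal half-life t of about 5 to 6 days (section 1.22). Assumption: one-compartment decline. The fraction of a dose's total AUC delivered in the first x days is 1 − 2^(−x/t).

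| | t = 5 days | t = 6 days |
|---|---|---|
| Dose 1, days 1–21 | 0.9456 | 0.9116 |
| Dose 1, days 17–21 | 0.0544 | 0.0691 |
| Dose 2, its first 5 days | 0.5000 | 0.4388 |
| Ratio over 21 days | (0.9456 + 0.5000)/0.9456 = 1.53 | (0.9116 + 0.4388)/0.9116 = 1.48 |
| Ratio over days 17–21 | (0.0544 + 0.5000)/0.0544 = 10.2 | (0.0691 + 0.4388)/0.0691 = 7.35 |

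These are exposure ratios, not DLT probabilities. The ratio for days 17–21 is large partly because one dose leaves little in those days.

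**Escalation probability**

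The table in 16.29b follows from P(escalate) = (1 − p)³ + 3p(1 − p)² × (1 − p)³, where p is the true DLT rate. All five of its values reproduce. The last three columns are illustrations and assume that every patient is redosed on day 17.

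- *16 days counted*: Cycle 1 ends at the second infusion and DLT onset is uniform over 21 days, so the observed rate is p × 16/21.
- *Added risk a*: all 21 days count and the second dose adds an independent risk a, so the rate is 1 − (1 − p)(1 − a).

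| True DLT rate | Plan | Reproduced | 16 days counted | a = 2 points | a = 10 points |
|---|---|---|---|---|---|
| 10% | 0.91 | 0.906 | 0.942 | 0.875 | 0.730 |
| 20% | 0.71 | 0.709 | 0.809 | 0.674 | 0.536 |
| 30% | 0.49 | 0.494 | 0.646 | 0.466 | 0.360 |
| 40% | 0.31 | 0.309 | 0.485 | 0.290 | 0.221 |
| 50% | 0.17 | 0.172 | 0.341 | 0.161 | 0.122 |

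The 21-day wording elsewhere makes days 17–21 best read as still Cycle 1, so the added-risk columns are the more natural case. Any extra second-dose toxicity then acts toward less escalation.

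**The case against.** The strongest reply is that the window permits early dosing without requiring it. The treatment tables say every 3 weeks, the evaluability rules ask for a completed cycle, and a careful phase I team may never dose early. It is true that the frequency is unknown. That limits the size of the problem, but it does not remove the permission.

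A second reply is that no section defines the DLT period as belonging to the first dose only. The second dose would be at the same assigned level, and 7.2 lets investigators, with the sponsor, declare some later events DLTs. Toxicity after a second dose is indeed informative about tolerability. But evaluability rests on one infusion of each drug and a 21-day cycle, and a discretionary clause does not restore a comparable observation period across patients.

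Third, the direction of the effect depends on whether days 17–21 count. This stands, as the table shows, and is a reason to fix the DLT period in days.

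Fourth, the calendar has no mid-cycle laboratory visit even with on-time dosing. Section 8.21 asks for clinical and laboratory review around each infusion, and section 15 asks for liver-test monitoring. The synopsis describes continuous safety monitoring, and section 8.0 tells patients to report symptoms at first occurrence. Symptomatic events would therefore surface. What remains is a gap for silent findings after day 17, such as the platelet, neutrophil and liver-test DLTs in 7.6, for which no scheduled check falls within the 21 days.

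Finally, the benefit warning in section 1.22 comes from single-agent data, with the responses in mesothelioma and ovarian cancer. It supports the stakes only indirectly.

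**Conclusion.** The concern holds and should be fixed. As written, a second infusion of both drugs on day 17 complies with the calendar. It leaves 16 rather than 21 days on the first dose alone and puts 5 of the 21 DLT days after two doses. These figures follow directly from the documents. The exposure ratios, about 1.5-fold over 21 days and 7- to 10-fold over days 17–21, rest on the assumed one-compartment decline and on dosing at the extreme edge of the window. The effect on the escalation probability cannot be determined, because the documents give neither the frequency of early dosing nor the timing of DLTs.

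**What to change.** In section 4.1, for phase I only, change the Cycle 2 Day 1 window to 0/+5 days. State that neither drug may be infused a second time before day 22, and that the end-of-cycle adverse-event and laboratory check takes place no earlier than day 21. The whole 21-day observation then follows one dose.

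As a clarification, state in 7.6 and 16.621 that the DLT period is days 1 to 21 from the first dose. It would also help to say in 4.1 whether later windows run from the nominal calendar or from the previous infusion.

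The cost is a wording change and slightly less scheduling freedom for sites at one phase I visit. No visits or patients are added.

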**Cockcroft-Gault Equation:**

$$\text{Creatinine clearance for males} = \frac{(140 - \text{age})(\text{weight in kg})}{(72)(\text{serum creatinine in mg/dL})}$$

$$\text{Creatinine clearance for females} = \frac{(140 - \text{age})(\text{weight in kg})(0.85)}{(72)(\text{serum creatinine in mg/dL})}$$

- ALT and AST  $\leq 2.5$  x ULN or  $\leq 5$  x ULN if liver metastases are present.
  - Total bilirubin  $\leq 1.5$  x ULN
- 3.28 Standard 12-lead ECG with the following parameters at screening (defined as the mean of the triplicate ECGs):
- QTcF interval at screening  $< 450$  msec (using Fridericia's correction)
- 3.29a Negative pregnancy test performed  $\leq 7$  days prior to registration (women of childbearing potential only).
- 3.29b Willing to return to enrolling institution for follow-up (during the Active Monitoring Phase of the study)
- 3.29c Willing to provide blood samples for correlative research purposes
- 3.3 Registration - Exclusion Criteria
- 3.31 Prior treatment with anti-PD-1, or anti-PD-L1 antibody which resulted in a patient having serious (grade 3-4) immune related adverse events.
- Note:
- Patients who have received prior treatment with anti-CTLA-4 may be enrolled, provided the following requirements are met:
    - Minimum of 12 weeks from the first dose of anti-CTLA-4 and  $>6$  weeks from the last dose
    - No history of severe immune-related adverse effects from anti-CTLA-4 (NCI CTCAE Grade 3 and 4)
- 3.32 More than one prior taxane regimen at any stage of the disease under study ("taxane" refers to paclitaxel, docetaxel, Abraxane® and cabazitaxel). Adjuvant and/or neoadjuvant treatments are considered together as one prior regimen.
- 3.33 Treatment with any other investigational agent or investigational device within 4 weeks prior to registration (or within five half-lives of the investigational product, whichever is longer). Patients must be  $\geq 2$  weeks since any investigational agent administered as part of a Phase 0 study (also referred to as an "early Phase I study" or "pre-Phase I study" where a sub-therapeutic dose of drug is administered) at the Coordinating Center PI's discretion, and should have recovered to eligibility levels from any toxicities.
- 3.34 Treatment with systemic immunostimulatory agents (including, but not limited to, interferon- $\alpha$  or interleukin-2) within 6 weeks or five half-lives of the drug (whichever is shorter) prior to registration.

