    - Screening CNS radiographic study  $\geq 4$  weeks from completion of radiotherapy and  $\geq 2$  weeks from discontinuation of corticosteroids
- 3.39a History of severe allergic, anaphylactic, or other hypersensitivity reactions to chimeric or humanized antibodies or fusion proteins
- 3.39b Patients who have a history or current evidence of bleeding disorder, i.e., any hemorrhage/bleeding event of CTCAE Grade  $\geq 2$ ,  $\leq 28$  days prior to registration.

- 3.39c History or current evidence of uncontrolled cardiovascular disease including, but not limited to, the following conditions:
- Congestive heart failure of New York Heart Association (NYHA, refer to appendix C) Class III or IV.
  - Unstable angina (symptoms of angina at rest) or new-onset angina  $\leq 6$  months before the start of anetumab ravtansine.
- 3.39d Uncontrolled intercurrent illness including, but not limited to, ongoing or active infection, symptomatic congestive heart failure, unstable angina pectoris, cardiac arrhythmia, or psychiatric illness/social situations that would limit compliance with study requirements.
- 3.39e Pregnant women are excluded from this study because atezolizumab is an investigational agent with the unknown potential for teratogenic or abortifacient effects. Note: Because there is an unknown but potential risk for adverse events in nursing infants secondary to treatment of the mother with atezolizumab, breastfeeding should be discontinued if the mother is treated with atezolizumab.
- 3.39f Patients on supraphysiologic doses of steroids or use of such  $\leq 6$  weeks prior to registration.
- 3.39g Known clinically significant liver disease, including active viral, alcoholic, or other hepatitis; cirrhosis; fatty liver; and inherited liver disease.

Note:

- Patients with past or resolved hepatitis B infection (defined as having a negative hepatitis B surface antigen [HBsAg] test and a positive anti-HBc [antibody to hepatitis B core antigen] antibody test) are eligible.
  - Patients positive for hepatitis C virus (HCV) antibody are eligible only if polymerase chain reaction (PCR) is negative for HCV RNA

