#### 6.23 Phase I and II

6.231 Documentation of IRB approval must be on file in the Registration Office before an investigator may register any patients.

In addition to submitting initial IRB approval documents, ongoing IRB approval documentation must be on file (no less than annually) at the Registration Office [REDACTED]. If the necessary documentation is not submitted in advance of attempting patient registration, the registration will not be accepted and the patient may not be enrolled in the protocol until the situation is resolved.

When the study has been permanently closed to patient enrollment, submission of annual IRB approvals to the Registration Office is no longer necessary.

6.232 At the time of registration, Registration/Randomization Application will verify the following:

- IRB approval
- Patient eligibility
- Existence of a signed consent form

6.233 At the time of registration, the following will be recorded:

- Patient has/has not given permission to store and use his/her sample(s) for future research at Mayo.
- Patient has/has not given permission to store and use his/her sample(s) for future research to learn, prevent, or treat other health problems.

6.234 Correlative Research

A mandatory correlative research component is part of this study, the patient will automatically be registered onto this component (see Section 14).

An optional correlative research component is part of this study, there will be an option to select if the patient is to be registered onto this component (see Section 17.0).

- Patient has/has not given permission to give his/her recurrence tissue sample for research testing
- 6.235 Consent and treatment on this protocol must commence at Mayo Clinic Rochester, Mayo Clinic Florida, or Mayo Clinic Arizona under the supervision of a medical oncologist.
- 6.236 Treatment cannot begin prior to registration and must begin  $\leq 28$  days after registration.
- 6.237 Screening tests/procedures (see Section 4.0) must be completed within the guidelines specified on the test schedule.
- 6.238 All required baseline symptoms (see Section 10.6) must be documented and graded.
- 6.239 Study drug is available on site

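### The pregnancy test is timed to registration only, so a negative result can be up to 35 days old at the first dose

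*Combined protocol and SAP*

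**What the plan says.** - **Eligibility (3.29a).** The item begins "Negative pregnancy test performed" and allows at most 7 days before registration, for women of childbearing potential only.
- **Calendar footnote 4 (4.1).** It repeats that limit with the same reference point: "Pregnancy test must be performed ≤7 days prior to registration".
- **Calendar row for the serum pregnancy test (4.1).** There is one mark, in the screening column. Cycle 1 Day 1, all later cycles and End of Treatment are blank.
- **Start of treatment (6.236).** "Treatment cannot begin prior to registration and must begin" within 28 days after registration.
- **Exclusion (3.39e).** "Pregnant women are excluded from this study because atezolizumab is an investigational agent", with teratogenic potential described as unknown. Section 1.2 describes the payload of the other drug, DM4, as a spindle poison.
- **Footnote 2 (4.1).** On the Cycle 1 Day 1 marks for hematology, chemistry and urinalysis it reads: "Need not be repeated if performed within 14 days of Cycle 1 Day 1". The coagulation panel has a Cycle 1 Day 1 mark with no such condition.

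**The concern.** The purpose of the pregnancy exclusion is to avoid fetal exposure, and exposure begins at the first dose, not at registration. A 7-day limit counted back from registration says nothing about the weeks that may follow. In that time a woman may conceive. A woman tested very early in pregnancy may also have had a negative result that a later test would have corrected. Either way she could be dosed with both agents without any scheduled test to show the pregnancy.

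The other provisions do not close the gap. Section 13.7 judges eligibility as it stood at registration, so a later conception does not make the patient ineligible. Sections 10.51 and 10.55 deal with reporting once a pregnancy has occurred. No passage available for review requires contraception.

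**Working it through.** **Inputs**

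- *t* = days from pregnancy test to registration: 0 to 7 (3.29a; footnote 4).
- *d* = days from registration to first dose: 0 to 28 (6.236).
- Scheduled repeat before the first dose: none (calendar row in 4.1).

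**Age of the test at first dose** = *t* + *d*

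- Minimum: 0 + 0 = 0 days.
- Maximum: 7 + 28 = 35 days.

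| Registration to first dose (*d*) | Age if tested on day of registration (*t* = 0) | Age if tested 7 days before (*t* = 7) |
|---|---|---|
| 0 days | 0 | 7 |
| 7 days | 7 | 14 |
| 14 days | 14 | 21 |
| 28 days | 28 | 35 |

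If treatment starts more than 7 days after registration, the test is more than 7 days old at first dose, however promptly it was done. At the latest permitted start it is at least 28 days old. The plan gives no figure of its own for this interval.

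**Comparison with the other screening tests**

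| Test | Rule at or near first dose | Maximum age at first dose |
|---|---|---|
| Hematology, chemistry | Repeated at Cycle 1 Day 1 unless recent (footnote 2) | 14 days |
| Coagulation panel (INR limit in 3.27) | Cycle 1 Day 1 mark, no condition | done at that visit |
| Eye examination | Counted back from start of treatment (footnote 7) | 28 days |
| Baseline scan | Counted back from Cycle 1 Day 1 (footnote 8) | 28 days, before any visit window |
| Pregnancy test | None | 7 + 28 = 35 days |
| ECG (QTcF limit in 3.28), echocardiogram | None; screening column allows 14 days before registration | 14 + 28 = 42 days |

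All the laboratory limits in 3.27 rest on hematology, chemistry or coagulation, so all are refreshed at Cycle 1 Day 1. Among the laboratory eligibility tests in the calendar, the pregnancy test has the shortest window before registration (7 days against 14) and is the only one with no link to treatment start.

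**Search for a repeat elsewhere.** The one general sentence about repeating tests closes the ophthalmology footnote (footnote 7). It concerns the eye tests, is discretionary and applies during treatment, so it cannot supply a test before the first dose.

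**The case against.** The strongest reply is that nothing here contradicts anything else. Criterion 3.29a, footnote 4 and the calendar row agree, and 6.236 can be followed alongside them. The 7 days were only ever a limit relative to registration. That is right, and a reader who infers an internal contradiction goes further than the text allows. What stands is a gap: a plan followed to the letter need not achieve what 3.39e is for.

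Other stronger readings are also unsupported:

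- **That the pregnancy test is the only screening test that can age.** The ECG and echocardiogram can be older still. The contrast holds for laboratory eligibility tests only.
- **That the protocol has no step at all at which a pregnancy could come to light.** History and examination are scheduled at Cycle 1 Day 1 and at each cycle. They are not a pregnancy test, but they are a contact. The consent pages were not available, and 10.51 shows that they may carry advice on avoiding pregnancy.
- **That a large share of patients is exposed to the gap.** Section 16.8 projects 29 women among 49 patients from general cancer-trial registrations. It gives no share of childbearing potential, so 29 is not an estimate of the number affected.
- **That the dose-finding would be damaged.** A patient who does not complete cycle 1 for reasons other than toxicity is replaced (13.6, 16.29a). No effect on the statistical design has been shown.

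It is also fair to say that a test nearer the first dose would narrow the gap without removing it. A very early pregnancy could still be missed, and later cycles would remain without a scheduled test.

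**Conclusion.** The point holds as a safety and eligibility gap. The plan permits a negative pregnancy test of any age from 0 to 35 days at first dose, while the laboratory tests behind 3.27 are refreshed at Cycle 1 Day 1. The 35 days follow from the two stated limits and need no outside assumption. They are the permitted extreme, and the documents do not show how often treatment starts late after registration or how many women are concerned. The conclusion assumes that the removed consent pages contain no repeat-test requirement, which cannot be checked. The primary endpoint, sample size and decision rules are unaffected.

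**What to change.** Reconcile 3.29a, footnote 4 and the pregnancy-test row of the calendar with the treatment-start window in 6.236, so that the recency limit is tied to the first dose (Cycle 1 Day 1) as well as to registration. Footnote 2 already provides a structure to copy: repeat at Cycle 1 Day 1 unless the last result is recent enough. The sponsor should set the interval; none is proposed here.

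The cost is amendment wording and at most one additional blood test. It applies only to women of childbearing potential whose test is out of window, at a visit where blood is already drawn for the coagulation panel.
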